6.3.1.12 Two Hours after Treatment Administration

- Collect blood for a PK sample
- Measure vital signs
- Record concomitant medications

6.3.1.13 Four Hours after Treatment Administration

- Collect blood for a PK sample
- Measure vital signs
- Record concomitant medications

6.3.1.14 Eight Hours after Treatment Administration

- Collect blood for a PK Sample
- Record concomitant medications
- Investigator visual skin assessment of the application sites
- Perform a physical examination

6.3.1.15 Twelve Hours after Treatment Administration

- Collect blood for a PK Sample
- Measure vital signs
- Record a 12-Lead ECG
- Determine if subject is stable for the next dosing period

- Record concomitant medications and adverse events

6.3.1.16 Twenty Four Hours after Treatment Administration

- Collect blood for a PK Sample
- Record concomitant medications and adverse events
- Investigator visual skin assessment of the application sites

6.3.1.17 Zolmitriptan PK Sample Handling

Details related to zolmitriptan PK sample collection and shipment is provided in [Appendix 2](#).

6.4 End of Study Visit/or Early Termination

- Within 48 hours after completion of all protocol required procedures on the last dosing day, subjects will complete an End of Study Visit. At that time, the following assessments will be performed:
- Record all AEs, whether observed by investigator, reported by the subject, observed in laboratory findings, or discovered by other means, on the AE CRF through the end of study final visit.
- Record a 12-Lead ECG
- Record any new concomitant medications and adverse events
- Measure vital signs (inclusive of temperature)
- Perform a physical examination
- Measure body weight
- Investigator visual skin assessment of the application sites
- Collect blood and urine for laboratory tests and serum pregnancy test (for all females)
- Discharge subject from the study

6.5 Post Study Phone Call - Follow-up on Adverse Events

Subjects must be called within 5-10 days following the day of discharge to follow-up on resolution of all ongoing AEs.

6.6 Early Termination

Subjects who terminate early will complete the assessments normally scheduled for the End of Study Visit and a post study phone call is required if any adverse events are ongoing at the time of discharge.

7 STUDY PROCEDURES

7.1 General Confinement Restrictions

Subjects will be required to stay in the clinic for the entire duration of the study (unless medically necessary to leave the clinic as instructed by the principal investigator and/or for non-medically related reasons considered on a case by case basis).

7.2 Collection, Processing and Assay of Samples

Each of the plasma samples collected for pharmacokinetic analysis will be separated into two containers. One of the samples will be sent to the analytical laboratory for analysis and one sample will be maintained at the investigative site until authorization is received from the sponsor to send the remaining samples to the bioanalytical lab. The plasma sample retained at the site may be used for further analysis (additional metabolites, etc.) at some future timepoint.

Subjects who complete all four treatments will have a blood draw volume of approximately 279 mL for the entire duration of the study (See Table below).

Blood Volume Requirements (mL)

Purpose	Expected Number	Sample Amount (in mL)	Total Amount (in mL)
Clinical laboratory tests (Chemistry, Serology, and Serum Pregnancy)	2	12	24.0
Serum Pregnancy (Admission/baseline and end of study)	2	3.5	7.0
Hematology	2	4.0	8.0
PK	60 (15 samples per period x 4 periods)	4.0	240.0
GRAND TOTAL			279 ml

7.3 Assessment Details

7.3.1 Clinical Laboratory Tests

Standard clinical laboratory tests (serum pregnancy for all women, chemistry, hematology, and urinalysis) will be performed at Screening and End of Study (or Early Termination) visit. A serum pregnancy test will also be completed for all women at the Admission/baseline visit.

Screening serological tests for HIV, Hepatitis B and Hepatitis C will be performed.

Hematology will include the following: Hematocrit, hemoglobin, red blood cell count, white blood cell count with differential, platelets, mean corpuscular volume, mean corpuscular hemoglobin, and mean corpuscular hemoglobin concentration.

Blood chemistry will include the following: Urea, glucose, aspartate aminotransferase (AST), alanine aminotransferase (ALT), alkaline phosphatase (AP), lactate dehydrogenase (LDH), sodium, phosphate, potassium, chloride, creatinine phosphokinase (CPK), globulin, cholesterol, creatinine, serum calcium, total bilirubin, triglyceride, cholesterol (HDL and LDL), gamma glutamyl transpeptidase (GGT) and uric acid.

Urinalysis will include the following: bilirubin, blood, glucose, ketones, leuokocyte esterase, nitrite, pH, protein, specific gravity, and urobilinogen. Microscopic examination will be conducted if protein, leukocyte esterase, nitrite and/or blood are detected.

Urine drug screen and alcohol testing will be performed at screening and the Admission/baseline visit. Urine drug screen will test for amphetamine, barbituates, cocaine, cannabinoids, phencyclidine (PCP), opioids, and methamphetamines.

Samples will be analyzed by a local laboratory. After reviewing the laboratory reports and evaluating the results, the Investigator must review, sign/date the laboratory report.

7.3.2 Vital Signs

Vital signs include pulse, respiratory rate, as well as systolic and diastolic arterial pressure. Vital signs will be recorded after subjects have been in the seated resting position for 2 minutes. Temperature will be taken at Screening, admission/baseline, and at end of study visit/or early termination only.

7.3.3 Electrocardiograms

A standard 12-lead ECG will be performed by a qualified individual at the site. General morphology and intervals [Heart rate, QRS, PR interval, QRS, QTn, QTcf], of interest will be assessed with each tracing. The principal or sub-investigator must review the tracing and assess it for any clinically significant abnormality. Any clinically significant ECG abnormality noted at the time of screening and/or pre-dose will be recorded in the appropriate source document and may result in the exclusion of the subject from the study.

7.3.4 Investigator Visual Skin Assessments of the Application Sites

Each M207 patch site (where a patch has been removed) will be observed for the following skin assessments pre-dose and immediately after removal of the patches from the subject's skin (and before swabbing) at 30 min, 60 min, 8 hr, 24 hr and at the End of Study/or Early Termination visit.

7.3.4.1 Erythema

The erythema evaluations will be performed using the following scale:

- 0 = None
- 1 = Mild redness
- 2 = Moderate colored redness
- 3 = Beet colored redness

7.3.4.2 Edema

The edema evaluations will be performed using the following scale:

- 0 = None
- 1 = Slight edema
- 2 = Moderate edema
- 3 = Severe edema

7.3.4.3 Bruising

Bruising assessments (visual rating) will be performed using the following scale:

- 0 = None
- 1 = $\leq 25\%$ application site has bruising spots
- 2 = ≥ 26 to $\leq 50\%$ application site has bruising spots
- 3 = $> 50\%$ application site has bruising spots

7.3.4.4 Bleeding

Bleeding will be assessed using the following scale:

- 0 = None
- 1 = Pink color on skin
- 2 = Visible blood drop
- 3 = Active bleeding

7.3.5 Residual Drug on Used M207 Patches

The used patches should be placed in the proper cryovial tube provided by Zosano and immediately placed on dry ice or frozen at approximately -80°C (plus or minus 10°C) and kept frozen until shipment to the bioanalytical lab. Used patches may be assayed for residual zolmitriptan if considered relevant after review of the pharmacokinetic results. Instructions for removing and storing the patches are provided in [Appendix 3](#).

7.3.6 Residual Drug on Skin after M207 Patch Removal

At the time patches are removed and after the investigator skin assessment (for all patch treatment groups), the M207 patch skin sites will be swabbed to collect any residual drug that may be on the skin surface where a transdermal M207 patch has been applied. The process consists of using 3 swabs to capture the drug residual for each patch site. The procedure is described in [Appendix 3](#).

7.3.7 Recording Adverse Events

Adverse events are collected from the time of first patch application until the end of the study (discharge from the clinic). A detailed discussion regarding the collection and reporting of adverse events is provided in [Section 8](#).

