5.2 Study Treatment Assignment and Schedule

The 24 subjects are planned to receive each of the four treatments (A, B, C, D) 48 hours apart. Subjects will be randomly assigned to one of 4 treatment sequences.

At the end of each dosing day, the safety data from the subjects will be evaluated. If tolerability is deemed to be acceptable by the Principal Investigator, a decision will be made to proceed to the next dosing day.

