6.3.1 Dosing Visit (all Periods) – All Treatments

The following procedures will be performed on each of the four dosing days. The actual procedures will be identical at each of the dosing days, only the study drug administered on each of the treatment days will vary.

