6.3.1.2 Treatment Administration (time 0 is application of second patch)

- Apply patches or administer intranasal zolmitriptan (see [Appendix 1](#) for instructions on patch administration)
- Begin recording all AEs, whether observed by investigator, reported by the subject, observed in laboratory findings, or discovered by other means, on the AE CRF through the End of Study (or Early Termination) final visit. All adverse events must be followed to resolution.

6.3.1.3 2 Minutes after Treatment Administration

- Collect blood for a PK sample
- Record concomitant medications

6.3.1.4 5 Minutes after Treatment Administration

- Collect blood for a PK sample
- Record concomitant medications

6.3.1.5 10 Minutes after Treatment Administration

- Collect blood for a PK sample
- Measure vital signs
- Record concomitant medications

6.3.1.6 15 Minutes after Treatment Administration

- Collect blood for a PK sample
- Record a 12-Lead ECG
- Record concomitant medications

6.3.1.7 20 Minutes after Treatment Administration

- Collect blood for a PK Sample
- Record concomitant medications

6.3.1.8 30 Minutes after Treatment Administration

- Collect blood for a PK sample following removal of the second patch
- Record concomitant medications and adverse events
- Remove patches and perform the following procedures in the order listed below:
 - Investigator visual skin assessment of the patch application sites within one minute of removing both patches and prior to swabbing
 - Retain and package patches for freezing. Refer to full instructions in [Appendix 3](#).

- Application site swabbing. Refer to full instructions in [Appendix 3](#).

6.3.1.9 45 Minutes after Treatment Administration

- Collect blood for a PK sample
- Record concomitant medications

6.3.1.10 60 Minutes after Treatment Administration

- Collect blood for a PK sample
- Measure vital signs
- Record concomitant medications and adverse events

6.3.1.11 90 Minutes after Treatment Administration

- Collect blood for a PK sample
- Record concomitant medications

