8 ADVERSE EVENTS

All skin and systemic AEs, regardless of treatment group or suspected causal relationship to the investigational products, will be reported as described in the following sections.

For all AEs, the Investigator must pursue and obtain information adequate both to determine the outcome of the AE and to assess whether it meets the criteria for classification as a SAE requiring immediate notification of the Sponsor. For all skin and systemic AEs, sufficient information should be obtained by the Investigator to determine the causality of the AE. The Investigator is required to assess causality. For skin and systemic AEs with a causal relationship to the investigational product, follow-up by the Investigator is required until the event or its sequelae resolve or stabilize at a level acceptable to the Investigator, and Zosano Pharma concurs with that assessment.

Reporting Period

Collection of skin and systemic AEs will be initiated from the time of treatment application and will conclude when the end of study procedures for the fourth treatment are completed (or Early Termination). The Investigator will also report to the Sponsor all SAEs that come to his/her attention after the study termination within 30 days of the last dose of study drug.

Any SAE occurring any time after the reporting period must be promptly reported if a causal relationship to the investigational product is suspected.

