8.2 Documentation and Reporting of Adverse Events By the Investigator

All adverse events (AEs) occurring after the application of the first dose through the End of study visit/or early termination, will be reported on the AE CRF pages. Based on the medical judgement of the investigator, all non-serious systemic and skin AEs will be followed until 30 days after the final end of study visit. All non-resolved, non-serious systemic and skin AEs beyond such date will be recorded as 'ongoing' without further follow up.

However, an AE form will not be filled out for subjects who sign the ICF but fail the entry criteria (Screening failures) during the Screening process and experience a non-serious AE.

Application site reactions will be reported on a dedicated assessment form for the visual skin assessment of the application sites. The regular AE form does not have to be completed for such events unless the events are not covered by the questions on the visual skin assessment form or are reported outside their time window. However, all such events will be included in the analyses of adverse event incidence.

Each AE, including skin AEs, is to be assessed to determine if it meets the criteria for an SAE. If an SAE occurs, expedited reporting will follow local and international regulations, as appropriate (See [Section 8.4](#)). It should be noted that the form for collection of SAE information is not the same as the AE CRF. Where the same data are collected, the forms must be completed in a consistent manner. For example, the same AE term should be used on both forms. Systemic and skin AEs should be reported using concise medical terminology on the CRF pages as well as on the form for collection of SAE information.

In addition to recording the signs, symptoms or diagnosis associated with them to describe the adverse event, the following will also be assessed and recorded:

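### Does dating adverse event collection from the first patch lose the events that follow a first-period nasal spray?

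*Protocol*

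**What the plan says.** Section 7.3.7 of the protocol is a short pointer on adverse events. It states that "Adverse events are collected from the time of first patch application until the end of the study (discharge from the clinic", and then that "A detailed discussion regarding the collection and reporting of adverse events is provided in" Section 8.

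Three other places set the start of collection:

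- Section 6.3.1.2, the administration step of the dosing visit, opens with "Apply patches or administer intranasal zolmitriptan" and continues with "Begin recording all AEs, whether observed by investigator, reported by the subject". Section 6.3.1, which governs this step, is headed as covering all treatments and says "The actual procedures will be identical at each of the dosing days".
- Section 8, under its reporting period: "Collection of skin and systemic AEs will be initiated from the time of treatment application".
- Section 8.2 requires reporting of all adverse events "occurring after the application of the first dose through the End of study visit/or early termination".

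Section 8.1 also uses patch wording: it counts clinically significant abnormal laboratory results from the day the study patch is applied. On the design, Section 5.2 says "Subjects will be randomly assigned to one of 4 treatment sequences", without listing the sequences.

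**The concern.** Treatment D involves no patch. A subject whose sequence begins with D has a first patch only in the second period, about 48 hours after the nasal dose. Read alone, Section 7.3.7 leaves the whole of that first period outside the collection window, and the laboratory sentence in Section 8.1 has the same defect.

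The second study objective compares the safety and tolerability of M207 with those of intranasal zolmitriptan, and Section 10.5 summarises treatment-emergent events by treatment. Events dropped under this rule could come only from D. The error would therefore run in one direction and make the nasal spray look better tolerated than it is. There is a further worry that an event arising in an unrecorded D period might be treated as pre-existing when the first patch is applied.

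**Working it through.** The protocol gives no figure to reproduce. The check is a comparison of texts, followed by the arithmetic of the worst case.

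**1. Start of collection for a subject who receives D first**

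- Section 7.3.7, read literally: the first patch, in period 2.
- Section 6.3.1.2: the nasal dose, in period 1.
- Section 8: treatment application, in period 1. The section's opening sentence covers events whatever the treatment group.
- Section 8.2: the first dose, in period 1.

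Section 7.3.7 is the exception among the four. The mismatch is real.

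**2. The instruction the site works from**

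Section 6.3.1.2 is the step-by-step instruction for dosing. It names the nasal spray, and recording begins in the next bullet. Section 6.3.1 repeats the same procedures on each dosing day, with event prompts at 30 minutes, 60 minutes, 12 hours and 24 hours. The general considerations in Section 6.3 also require all adverse events on dosing days to be documented. Losing a D-first subject's events would mean setting all of this aside in favour of one summary sentence that refers to Section 8 for its detail.

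**3. How the protocol uses patch wording**

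- Section 4.1 measures the 48-hour spacing of all four doses from patch application.
- Section 6 defines time 0 for the washout after each dose as application of the patches.
- Section 6.3 withholds breakfast until two hours after patch application, on days when A, B, C or D may be given.
- Section 10.3 times early drop-out from patch application.

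Each of these rules must cover nasal-spray days too. Section 7.3.7 follows the same habit.

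**4. The pre-existing condition argument**

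Section 8.1 treats a condition as pre-existing if it was present before study treatment started. A first nasal dose is study treatment, so an event after it does not qualify.

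**5. The laboratory sentence in Section 8.1**

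Under Section 7.3.1, scheduled safety laboratory tests after screening occur only at the End of Study or Early Termination visit. For anyone who completes, that visit follows every patch period. Only an unscheduled test, or a subject who leaves after D and before any patch, could be touched.

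**6. Size of the worst case**

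Inputs: 24 subjects (Section 4.4) and 4 sequences (Section 5.2). Assumptions: equal allocation, exactly one sequence starting with D, no event recorded in those first periods, one incidence *p* across periods, and all 24 subjects kept in the denominator.

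- D-first subjects: 24 / 4 = 6, or 6 / 24 = 25% of D periods.
- Observed incidence under D: *p* × 18 / 24. For illustration, *p* = 0.20 gives 0.15 and *p* = 0.40 gives 0.30.

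Because the sequences are not listed, the number of D-first subjects could in principle lie anywhere from 0 to 24. The incidences of 0.20 and 0.40 are not in the protocol. These figures describe what would happen if Section 7.3.7 displaced every other instruction. Steps 2 and 3 give no reason to expect that.

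**The case for a change.** The best argument for the concern is that the protocol itself fixes the start of collection and does so inconsistently, so this is not a detail left for the analysis plan. Section 7.3.7 refers to Section 8 without saying that Section 8 prevails. Reading the phrase as the first of the two patches in a dose does not help, since a D period would then have no start at all. The patch wording recurs in Section 8.1, so it is more than one stray word. The sharpest case is a subject who receives D first and withdraws. That subject never has a patch, so Section 7.3.7 never opens, yet Section 10.3 places the subject in the Safety Population.

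The inconsistency of wording stands. The consequence does not. The early withdrawal is covered by Section 6.3.1.2 from the nasal dose and by Section 8.2 from first dose to early termination. The one-directional bias needs events actually to go unrecorded, and the operative instructions require them to be recorded. The suggestion that drug-naive subjects report most in period 1 has no support in the protocol, and the incidence calculation above does not use it. Rewording Section 7.3.7 would add no data beyond what Sections 6.3.1.2, 8 and 8.2 already require.

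**Conclusion.** This is a clerical slip. Section 7.3.7, and the laboratory sentence in Section 8.1, say patch where they mean study treatment. The sections that direct collection and reporting start at administration of whichever treatment is given, so the events summarised for D should cover the same kind of window as those for A, B and C. No loss of events and no bias for or against D is shown. The 25% figure and the incidence shifts depend on an assumed set of sequences and on complete non-recording, and should not be carried forward as an estimate.

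The conclusion assumes that the site follows the dosing-day procedures in Section 6.3.1 as written. On that footing, tidier wording would change neither the data collected nor the safety comparison, and no change to the plan is called for.

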8 ADVERSE EVENTS

All skin and systemic AEs, regardless of treatment group or suspected causal relationship to the investigational products, will be reported as described in the following sections.

For all AEs, the Investigator must pursue and obtain information adequate both to determine the outcome of the AE and to assess whether it meets the criteria for classification as a SAE requiring immediate notification of the Sponsor. For all skin and systemic AEs, sufficient information should be obtained by the Investigator to determine the causality of the AE. The Investigator is required to assess causality. For skin and systemic AEs with a causal relationship to the investigational product, follow-up by the Investigator is required until the event or its sequelae resolve or stabilize at a level acceptable to the Investigator, and Zosano Pharma concurs with that assessment.

Reporting Period

Collection of skin and systemic AEs will be initiated from the time of treatment application and will conclude when the end of study procedures for the fourth treatment are completed (or Early Termination). The Investigator will also report to the Sponsor all SAEs that come to his/her attention after the study termination within 30 days of the last dose of study drug.

Any SAE occurring any time after the reporting period must be promptly reported if a causal relationship to the investigational product is suspected.

8.1 Adverse Event Definitions

An AE is any untoward medical event that occurs in a clinical investigation, where a subject is administered a product or medical device, without regard to causal relationship between the event and the treatment. An AE can be any unfavorable and unintended sign or symptom, including clinically significant laboratory values and test results, concomitant illness, accident, or worsening of an existing medical condition.

Information about all adverse events, whether volunteered by the subject, discovered by investigator questioning, or detected through physical examination, laboratory or other means, will be collected and recorded on the Adverse Event CRF using the signs, symptoms or diagnosis associated with them and followed until resolution or, in the Investigator's opinion, a stable condition is reached, or until the patient is lost to follow up.

Medical conditions/diseases present before starting study treatment are only considered adverse events if they worsen after starting study treatment.

In the event of a clinically important AE, a blood sample may be collected as soon as possible after the occurrence of the event for drug assay or for additional laboratory tests. The Investigator will ensure that the serum sample is properly labeled and stored. The Investigator and other study personnel responsible for the care of the patient will institute any supplementary investigations of significant AEs based on the clinical judgment of the likely causative factor(s). This may include seeking further opinion of a specialist in the field of the AE.

Any abnormal lab tests starting from the day of study patch application that are clinically significant, as determined by the Investigator, should be reported as AEs if:

- the test result is associated with accompanying symptoms;
- the test result requires additional diagnostic testing or medical/surgical intervention;
- the test result leads to a change in study dosing or discontinuation from the study, significant additional concomitant drug treatment, or other therapy;
- the test result is considered to be an AE by the Investigator or sponsor

Merely repeating an abnormal test, in the absence of any of the above conditions, does not constitute an AE. Any abnormal test result that is determined to be an error does not require reporting as an AE.

